10.3 Data Analysis Plans

Analysis of primary endpoint, late toxicity rates, to decide whether to reject the null hypothesis, will be conducted as described above. In addition, the estimated acute and late toxicity rates will be reported with 95% confidence intervals in the final analysis.

As per the analyses of secondary outcomes, binary outcomes like (1) 2 and 5 years biochemical control according to the Phoenix criteria; (2) local recurrence rate after 2 and 5 years (defined by biopsy); and (3) rate of screened to truly included patients and compliance with dose restrictions, will be summarized by estimated proportions and associated 95% confidence intervals. Numerical outcomes like (4) quality of life (according to EPIC-26 and PCSI) will be summarized using descriptive (mean and standard deviation, median and range) statistics. Exploratory

correlation analyses will be conducted to identify biomarkers correlated with the diagnosis and the course of the disease, as well as gastrointestinal and urogenital toxicity.

In the event of an early termination of this study, the same analysis plan as described above will be followed, but based on the data available at the time of study termination.

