3.3 Exploratory Objectives

4.0 STUDY ENDPOINTS

4.1 Primary

The planning criteria that will be used are the current standard of care and standard practice at UNC and includes defined treatment volumes with a prescribed dose while respecting the dose constraints to all organs at risk. The primary endpoint is grade 3+ late genitourinary toxicity and gastrointestinal toxicity as classified and graded according to the National Cancer Institute's Common Terminology Criteria for Adverse Events (CTCAE), version 5.0 at 12 months after radiation therapy.

- 4.2 Secondary
- 4.2.1 Grade 3+ acute and late genitourinary and gastrointestinal toxicity will be defined according to CTCAE, version 5.0 during radiation therapy and at 1, 3, 6, 9, 12, 18, 24, 30, 36, 42, 48, 54 and 60 months post radiotherapy. Additionally, this will be reported as a cumulative incidence over the entire 5-year course of the study.
- 4.2.2 Biochemical control will be defined according to the Phoenix criteria³³ (PSA rise of 2 ng/mL over nadir) at 2 and 5 years after radiation therapy.
- 4.2.3 Patient reported quality of life will be measured using the Expanded Prostate Cancer Index Composite (EPIC-26) and the Urinary Obstruction/Irritation scale of the validated Prostate Cancer Symptom Indices (PCSI). Patient reported quality of life will be measured before the start of radiation therapy at 1, 3, 6, 9, 12, 18, 24, 30, 36, 42, 48, 54, and 60 months post radiotherapy.
- 4.2.4 The total number of subjects enrolled on the study will be compared to the total number of screened subjects.
- 4.2.5 The feasibility of meeting dose constraints will be defined as the proportion of subjects who meet the following dose constraint criteria:
 - SBRT-CK boost dose prescription: 6.5Gy x 3
 - PTV: V19.5Gy > 95%
 - PTVmax > 150%, CI < 1.8
 - CTV: V19.5Gy > 99%
 - \circ DIL: V24.0Gy > 99%

- SBRT-CK boost dose constraints:
 - o Rectum
 - V21.1Gy< 5 %
 - V18.9Gy< 20 %
 - V17.5Gy<10 %
 - V16.2Gy< 40 %
 - V10.2Gy< 60 %
 - V9.3Gy< 40 %
 - V19.5Gy<1cc
 - Max<21.2Gy
 - Bladder
 - V21.1Gy< 5 %
 - V19.5y < 5 cc
 - V9.3Gy<40 %
 - Max<21.2Gy
 - Prostatic Urethra
 - V19.5Gy > 95%
 - V22Gy < 0.03cc
 - Membranous Urethra
 - V18 Gy < 50%
 - Large bowel
 - V15Gy<1cc
 - Small bowel
 - V15Gy<1cc
 - Penile bulb
 - V15Gy< 3cc

4.2.6 Performance of PSMA-PET/MRI to PSMA PET/CT as defined as:

- Rate of identification and delineation of DIL (e.g. sensitivity and specificity)

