6.4 Definition of Dose Limiting Toxicity

A dose-limiting toxicity is defined as all Grade 3 or above acute toxicities attributed to the treatment under study. The accrual will be halted if the number of patients with dose-limiting toxicities equals to or exceeds a rate of 30%.

6.5 **Duration of Follow Up**

All patients will be followed for up to 5 years after radiation, or until death, whichever occurs first, after removal from study treatment for determination of study endpoints. Patients removed from study treatment for unacceptable adverse events (AEs) will be followed for resolution or stabilization of the AEs. All patients (including those withdrawn for AEs) should be followed after removal from study treatment as stipulated in the protocol.

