7.1.5 Disease Assessment

Patients' disease will be assessed with prostate-specific antigen (PSA) test draws. PSA will be obtained at within three months prior to study enrollment and then at each follow up (1, 3, 6, 9, 12, 18, 24, 30, 36, 42, 48, 54, and 60 months post treatment).

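### Biochemical control at 2 and 5 years is planned as a simple proportion with no rule for incomplete follow-up; a time-to-event estimate is needed, above all at early closure

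*Combined protocol and SAP*

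**What the plan says.** Section 4.2.2 defines biochemical control by the Phoenix criteria, to be assessed "at 2 and 5 years after radiation therapy". Section 10.3 begins its account of the secondary analyses with "binary outcomes like (1) 2 and 5 years biochemical control according to the Phoenix criteria" and says that such outcomes "will be summarized by estimated proportions and associated 95% confidence intervals". For this endpoint it names no denominator, no interval method, no censoring rule, no rule for death before failure and no time-to-event method. By contrast, Section 4.2.1 promises a cumulative incidence over five years for toxicity.

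Amendment 6, which supports early closure, added the last paragraph of Section 10.3: on early termination "the same analysis plan as described above will be followed, but based on the data available at the time of study termination".

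Three other sections bear on follow-up:
- Section 6.5: "All patients will be followed for up to 5 years after radiation, or until death, whichever occurs first".
- Section 7.1.5: "PSA will be obtained at within three months prior to study enrollment and then at each follow up", with 13 post-treatment visits from 1 to 60 months.
- Section 6.6 lets the investigator remove patients because the study is closing. Sections 6.7 and 6.8 cover loss to follow-up and withdrawal.

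**The concern.** Biochemical failure happens at a point in time, and not every man will be observed to 2 or 5 years. Entry is staggered (Section 2.1 plans 24 months of recruitment), some men will be lost or die, and the study is closing early. A proportion then depends on who is counted:
- Keeping every man in the denominator treats those not yet followed as controlled, which pushes the estimate up.
- Counting only failures and men who reached the landmark keeps early failures and drops men censored while still controlled, which pushes it down.
- Counting only men whose potential follow-up reaches the landmark is unbiased under independent censoring, but discards everyone else.

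The plan chooses none of these, so the choice could be made after the data are seen. At stake is whether a reported percentage can be interpreted, and whether partial follow-up, which may be most of what a closed study has, is used at all.

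**Working it through.** **Stated figures.** The documents give no sample size, power or precision for biochemical control, so there is no figure of the plan's own to reproduce.

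**Inputs.**
- 5-year control of 83%: the recurrence-free survival in Section 2.4, used here as the true value.
- 42 men, 10% loss, 21 months of accrual: Sections 10.1 and 10.2.
- Assumed: exponential failure times, independent loss, uniform accrual, radiation ending 4 months after enrolment.

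**Formulas.** The failure rate is λ = −ln(0.83)/5 = 0.0373 per year, so 2-year control is exp(−2λ) = 92.8%. With loss rate g:
- observed failures by 5 years: F = λ/(λ+g) × [1 − exp(−5(λ+g))]
- men reaching 5 years failure-free: R = exp(−5(λ+g))
- everyone in the denominator: 1 − F
- failures plus completers: R/(R+F)

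**5-year control, true value 83.0%**

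| Loss | R | F | Everyone | Failures plus completers |
|---|---|---|---|---|
| 10% in total over 5 years | 0.83 × 0.90 = 0.747 | 0.162 | 83.8% | 82.2% |
| 5% per year (assumed) | 0.83 × 0.95^5 = 0.642 | 0.151 | 84.9% | 81.0% |
| 10% per year (assumed) | 0.83 × 0.90^5 = 0.490 | 0.133 | 86.7% | 78.6% |

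The bias is under 1 point each way in the first row and about 4 points each way in the last. In 4,000 simulated trials of 42 men, Kaplan-Meier averaged 83.0% with 10% total loss and 82.9% with 10% per year.

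**2-year control if the study closes 36 months after its start (assumed), true value 92.8%.** Post-radiation follow-up is 36 − 4 − U = 32 − U months, with entry time U uniform on 0 to 21. Two years is reached when U ≤ 8, which is 8/21 = 38.1% of men, or 16 of 42.
- Failure-free at 2 years: 0.381 × 0.928 = 0.354.
- Observed failures: 0.381 × 0.0718 = 0.027 among these men. The other 13/21, followed 11 to 24 months, have an average failure probability of 0.0528 and add 0.619 × 0.0528 = 0.033. The total is 0.060.
- Everyone: 1 − 0.060 = 94.0%.
- Failures plus completers: 0.354/(0.354 + 0.060) = 85.5%, about 7 points low.

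The simulation gave 93.9% and 85.4%, against 92.8% for Kaplan-Meier.

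**Closure 24 months after the start (assumed).** The longest follow-up is 24 − 4 = 20 months, so nobody reaches 2 years. The two proportions become 97.1% and 0%, the potential-follow-up denominator is empty, and Kaplan-Meier has no value at 24 or 60 months.

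**The documents' own dates.** From 1 January 2023 (the planned start month, Section 2.1) to 24 July 2024 (the Amendment 6 version date) is 570 days, or 18.7 months. Taking off about 2 months of radiation (Section 10.1) leaves 16.7 months. Taking off about 8 weeks of ADT beforehand (Section 8.1) leaves 14.9. If both dates held as first entry and cutoff, no man could have reached 24 months.

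**Overlap with ADT.** Section 2.4 describes a usual ADT course of 18 months. About 2 months before radiation and 2 months during it leave roughly 18 − 4 = 14 months afterwards, so nearly all of a 15-month curve would come from men still on ADT.

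**The case against.** The other side has five fair points.

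- **A missing rule is not yet a bias.** A reader might infer that any proportion here is biased, or that its confidence interval has the wrong denominator. The documents support neither: they state no denominator and no interval method, and the potential-follow-up denominator is unbiased under independent censoring. This limits the claim, but the choice is still left open.
- **With full follow-up the effect is small.** The only loss figure in the documents is 10%, which gives a bias of about 1 point or less. The 95% half-width at 83% of 42 men is 1.96 × √(0.83 × 0.17/42), about 11 points, so even a 4-point bias lies well inside it. This stands for the planned course of the study. The 10% belongs to the 12-month primary endpoint, however, so loss by 5 years could be higher.
- **PSA data may outlast withdrawal.** Section 6.8 asks withdrawing patients to allow record abstraction for biochemical control, and Section 8.7 calls PSA follow-up routine. This reduces loss, but does not help men who have not reached the landmark when data collection stops.
- **The closure dates are not established.** January 2023 is a plan and July 2024 is an amendment date. First enrolment, number enrolled and data cutoff are not given, and removal at closure is discretionary. An empty 2-year denominator is therefore conditional.
- **Kaplan-Meier cannot restore the landmarks.** On those dates it gives no 2- or 5-year estimate either, and a 12-month figure would fall largely within ADT. This stands and shapes the fix.

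**Conclusion.** The point holds as a weakness of method. Section 10.3 applies a fixed-time proportion to an outcome with incomplete follow-up, and keeps it for early termination, where it fits worst.

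The size depends on follow-up: negligible to small at 5 years as planned, about 4 points in either direction under assumed heavy loss, and about 7 points low at 2 years for failures plus completers under an assumed 36-month closure. It is degenerate if nobody reaches the landmark. These figures rest on exponential failure, independent censoring and uniform accrual.

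A reader might go further and conclude that no man in this study reached 2 years. The documents do not show that: an earlier first entry or a later cutoff would let some men reach the landmark. This is a descriptive secondary endpoint, and the primary toxicity test is unaffected. The change should still be made.

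**What to change.** Replace the biochemical-control item in Section 10.3 with the following:

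1. The endpoint is time from the end of radiation to Phoenix failure, censored at the last PSA.
2. State how death without failure is handled: as a competing event (cumulative incidence) or as part of a composite.
3. Estimate freedom from failure by Kaplan-Meier, or failure by cumulative incidence, with 95% confidence intervals and numbers at risk. Give 2- and 5-year values only where follow-up supports them.
4. At early termination, report the curve descriptively up to the last time with adequate numbers at risk, by a minimum set in advance. Report no later landmark, and note that early estimates come largely from men still on ADT.

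The cost is a few sentences of text and standard programming. PSA is already scheduled at 13 post-treatment visits, so no new data are needed. The method relies on non-informative censoring, which the report should acknowledge.

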11.0 STUDY MANAGEMENT

11.1 Institutional Review Board (IRB) Approval and Consent

It is expected that the IRB will have the proper representation and function in accordance with federally mandated regulations. The IRB should approve the consent form and protocol.

In obtaining and documenting informed consent, the investigator should comply with the applicable regulatory requirement(s) and should adhere to Good Clinical Practice (GCP) and to ethical principles that have their origin in the Declaration of Helsinki.

Before recruitment and enrollment onto this study, the patient will be given a full explanation of the study and will be given the opportunity to review the consent form. Each consent form must include all the relevant elements currently required by the FDA Regulations and local or state regulations. Once this essential information has been provided to the patient and the investigator is assured that the patient understands the implications of participating in the study, the patient will be asked to give consent to participate in the study by signing an IRB-approved consent form.

Prior to a patient's participation in the trial, the written informed consent form should be signed and personally dated by the patient and by the person who conducted the informed consent discussion.

11.2 Required Documentation

Before the study can be initiated at any site, the following documentation must be provided to the LCCC Study Coordinator.

- A copy of the official IRB approval letter for the protocol and informed consent
- IRB membership list
- CVs and medical licensure for the principal investigator and any subinvestigators who will be involved in the study.
- CAP and CLIA Laboratory certification numbers and institution lab normal values

11.3 Registration Procedures

All subjects must be registered with the Lineberger Comprehensive Cancer Center via $OnCore^{$ [®]}.

11.4 Data Management and Monitoring/Auditing

The Department of Radiation Oncology will serve as the coordinating center for this trial. Data will be collected through a web based clinical research platform, OnCore[®].

The sponsor will provide direct access to source data/documents for trial-related monitoring, audits, IRB/IEC review, and regulatory inspection. As an investigator initiated study, this trial will also be audited by the LCCC compliance committee every six or twelve months. It will also be monitored according to LCCC SOPs, within 8 weeks of the first patient enrolled, and subsequently every 4 months while there are subjects in the treatment period. Monitoring will occur annually once the study is closed to accrual and all subjects are in the follow-up period.

11.5 Adherence to the Protocol

Except for an emergency situation in which proper care for the protection, safety, and well-being of the study patient requires alternative treatment, the study shall be conducted exactly as described in the approved protocol.

11.5.1 Emergency Modifications

UNC investigators may implement a deviation from, or a change of, the protocol to eliminate an immediate hazard(s) to trial subjects without prior UNC or their respective institution's IRB/IEC approval/favorable opinion.

11.5.2 Single Patient/Subject Exceptions

Eligibility single subject exceptions are not permitted for Lineberger Comprehensive Cancer Center Investigator Initiated Trials under any circumstances. Other types of single subject exceptions may be allowed if proper regulatory review has been completed in accordance with Lineberger Comprehensive Cancer Center's Single Subject Exceptions Policy.

11.5.3 Other Protocol Deviations/Violations

According to UNC's IRB, a protocol deviation is any unplanned variance from an IRB approved protocol that:

- Is generally noted or recognized after it occurs
- Has no substantive effect on the risks to research participants
- Has no substantive effect on the scientific integrity of the research plan or the value of the data collected
- Did not result from willful or knowing misconduct on the part of the investigator(s).

An unplanned protocol variance is considered a violation if the variance meets any of the following criteria:

- Has harmed or increased the risk of harm to one or more research participants.
- Has damaged the scientific integrity of the data collected for the study.
- Results from willful or knowing misconduct on the part of the investigator(s).
- Demonstrates serious or continuing noncompliance with federal regulations, State laws, or University policies.

If a deviation or violation occurs please follow the guidelines below:

Protocol Deviations: UNC personnel will record the deviation in OnCore[®], and report to any sponsor or data and safety monitoring committee in accordance with their policies.

Protocol Violations: Violations should be reported by UNC personnel within one (1) week of the investigator becoming aware of the event using the same IRB online mechanism used to report Unanticipated Problems.

Unanticipated Problems:

Any events that meet the criteria for "Unanticipated Problems" as defined by UNC's IRB must be reported by the study personnel using the IRB's web-based reporting system.

11.6 Amendments to the Protocol

Should amendments to the protocol be required, the amendments will be originated and documented by the Principal Investigator at UNC. It should also be noted that when an amendment to the protocol substantially alters the study design or the potential risk to the patient, a revised consent form might be required.

11.7 Record Retention

Study documentation includes all eCRFs, data correction forms or queries, source documents, Sponsor correspondence to Investigators, monitoring logs/letters, and regulatory documents (e.g., protocol and amendments, IRB correspondence and approval, signed patient consent forms).

Source documents include all recordings of observations or notations of clinical activities and all reports and records necessary for the evaluation and reconstruction of the clinical research study.

Government agency regulations and directives require that all study documentation pertaining to the conduct of a clinical trial must be retained by the study investigator. In the case of a study with a drug seeking regulatory approval and marketing, these documents shall be retained for at least two years after the last approval of marketing application in an International Conference on Harmonization (ICH) region. In all other cases, study documents should be kept on file until three years after the completion and final study report of this investigational study.

11.8 Obligations of Investigators

The Principal Investigator is responsible for the conduct of the clinical trial at the site in accordance with Title 21 of the Code of Federal Regulations and/or the Declaration of Helsinki. The Principal Investigator is responsible for personally overseeing the treatment of all study patients. The Principal Investigator must assure that all study site personnel, including sub-investigators and other study staff members, adhere to the study protocol and all FDA/GCP/NCI regulations and guidelines regarding clinical trials both during and after study completion.

At the completion of the study, all eCRFs will be reviewed by the Principal Investigator and will require his/her final signature to verify the accuracy of the data.

13.0 APPENDICES

A.1 NCCN Risk Stratification

Unfavorable intermediate risk disease:

- T2b-T2c OR
- Gleason score 3+4=7/grade group 2 or Gleason score 4+3=7/grade group 3 OR
- PSA 10-20 ng/mL

High risk disease:

- T3a OR
- Gleason score 8/grade group 4 or Gleason score 4+5=9/grade group 5 OR
- PSA>20 ng/mL

A.2. ECOG Performance Status

ECOG Performance Status

Developed by the Eastern Cooperative Oncology Group, [name], Group Chair.*

GRADE	ECOG PERFORMANCE STATUS
0	Fully active, able to carry on all pre-disease performance without restriction
1	Restricted in physically strenuous activity but ambulatory and able to carry out work of a light or sedentary nature, e.g., light house work, office work
2	Ambulatory and capable of all selfcare but unable to carry out any work activities; up and about more than 50% of waking hours
3	Capable of only limited selfcare; confined to bed or chair more than 50% of waking hours
4	Completely disabled; cannot carry on any selfcare; totally confined to bed or chair
5	Dead

A.3 Toxicity according to CTCAE

Common Terminology Criteria for Adverse Events (CTCAE v5) Source: https://evs.nci.nih.gov/ftp1/CTCAE/About.html

MedDRA Code	202 45004 500	CTCAE Term	Grade 1	Grade 2	Grade 3	Grade 4	Grade 5
10002153	Gastrointestinal disorders	Anal fissure	Asymptomatic	Symptomatic	Invasive intervention indicated		- Grade 5
10002156	Gastrointestinal disorders	Anal fistula	Asymptomatic	Symptomatic, invasive intervention not indicated	Invasive intervention indicated	Life-threatening consequences; urgent intervention indicated	Death
10055226	Gastrointestinal disorders	Anal hemorrhage	Mild symptoms; intervention not indicated	Moderate symptoms; intervention indicated	Transfusion indicated; invasive intervention indicated; hospitalization	Life-threatening consequences; urgent intervention indicated	Death
10065721	Gastrointestinal disorders	Anal mucositis	Asymptomatic or mild symptoms; intervention not indicated	Symptomatic; medical intervention indicated; limiting instrumental ADL	Severe symptoms; limiting self care ADL	-	-
10065722	Gastrointestinal disorders	Anal necrosis	-	-	TPN or hospitalization indicated; invasive intervention indicated	Life-threatening consequences; urgent operative intervention indicated	Death
10002167	Gastrointestinal disorders	Anal pain	Mild pain	Moderate pain; limiting instrumental ADL	Severe pain; limiting self care ADL		-
10002176	Gastrointestinal disorders	Anal stenosis	Asymptomatic; clinical or diagnostic observations only; intervention not indicated	Symptomatic; altered GI function	Symptomatic and severely altered GI function; non-emergent operative intervention indicated; TPN or hospitalization indicated	Life-threatening consequences; urgent operative intervention indicated	Death
10002180	Gastrointestinal disorders	Anal ulcer	Asymptomatic; clinical or diagnostic observations only; intervention not indicated	Symptomatic; altered GI function	Severely altered GI function; TPN indicated; elective invasive intervention indicated	Life-threatening consequences; urgent operative intervention indicated	Death
10009995	Gastrointestinal disorders	Colonic fistula	Asymptomatic	Symptomatic, invasive intervention not indicated	Invasive intervention indicated	Life-threatening consequences; urgent intervention indicated	Death
10009998	Gastrointestinal disorders	Colonic hemorrhage	Mild symptoms; intervention not indicated	Moderate symptoms; intervention indicated	Transfusion indicated; invasive intervention indicated; hospitalization	Life-threatening consequences; urgent intervention indicated	Death
10010000	Gastrointestinal disorders	Colonic obstruction	Asymptomatic; clinical or diagnostic observations only; intervention not indicated	Symptomatic; altered GI function	Hospitalization indicated; invasive intervention indicated	Life-threatening consequences; urgent operative intervention indicated	Death
10010001	Gastrointestinal disorders	Colonic perforation	-	Invasive intervention not indicated	Invasive intervention indicated	Life-threatening consequences; urgent intervention indicated	Death
10010004	Gastrointestinal disorders	Colonic stenosis	Asymptomatic; clinical or diagnostic observations only; intervention not indicated	Symptomatic; altered GI function	Severely altered GI function; tube feeding or hospitalization indicated; elective operative intervention indicated	Life-threatening consequences; urgent operative intervention indicated	Death
10010006	Gastrointestinal disorders	Colonic ulcer	Asymptomatic; clinical or diagnostic observations only; intervention not indicated	Symptomatic; altered GI function	Severely altered GI function; TPN indicated; elective invasive intervention indicated	Life-threatening consequences; urgent operative intervention indicated	Death
10010774	Gastrointestinal disorders	Constipation	Occasional or intermittent symptoms; occasional use of stool softeners, laxatives, dietary modification, or enema	Persistent symptoms with regular use of laxatives or enemas; limiting instrumental ADL	Obstipation with manual evacuation indicated; limiting self care ADL	Life-threatening consequences; urgent intervention indicated	Death
10012727	Gastrointestinal disorders	Diarrhea	Increase of <4 stools per day over baseline; mild increase in ostomy output compared to baseline	Increase of 4 - 6 stools per day over baseline; moderate increase in ostomy output compared to baseline; limiting instrumental ADL	Increase of >=7 stools per day over baseline; hospitalization indicated; severe increase in ostomy output compared to baseline; limiting self care ADL	Life-threatening consequences; urgent intervention indicated	Death
10036774	Gastrointestinal disorders	Proctitis	Rectal discomfort, intervention not indicated	Symptomatic (e.g., rectal discomfort, passing blood or mucus); medical intervention indicated; limiting instrumental ADL	Severe symptoms; fecal urgency or stool incontinence; limiting self care ADL	Life-threatening consequences; urgent intervention indicated	Death
10064993 10038062	Gastrointestinal disorders Gastrointestinal disorders	Rectal fissure Rectal fistula	Asymptomatic	Symptomatic Symptomatic, invasive intervention not indicated	Invasive intervention indicated Invasive intervention indicated	- Life-threatening consequences; urgent intervention indicated	- Death
10038064	Gastrointestinal disorders	Rectal hemorrhage	Mild symptoms; intervention not indicated	Moderate symptoms; intervention indicated	Transfusion indicated; invasive intervention indicated; hospitalization	Life-threatening consequences; urgent intervention indicated	Death
10063190	Gastrointestinal disorders	Rectal mucositis	Asymptomatic or mild symptoms; intervention not indicated	Symptomatic; medical intervention indicated; limiting instrumental ADL	Severe symptoms; limiting self care ADL	Life-threatening consequences; urgent operative intervention indicated	Death
10065709	Gastrointestinal disorders	Rectal necrosis	-	-	Tube feeding or TPN indicated; invasive intervention indicated	Life-threatening consequences; urgent operative intervention indicated	Death
10065707	Gastrointestinal disorders	Rectal obstruction	Asymptomatic; clinical or diagnostic observations only; intervention not indicated	Symptomatic; altered GI function; limiting instrumental ADL	Hospitalization indicated; invasive intervention indicated; limiting self care ADL	Life-threatening consequences; urgent operative intervention indicated	Death
10038072	Gastrointestinal disorders	Rectal pain	Mild pain	Moderate pain; limiting instrumental ADL	Severe pain; limiting self care ADL	-	-
10038073	Gastrointestinal disorders	Rectal perforation	-	Invasive intervention not indicated	Invasive intervention indicated	Life-threatening consequences; urgent operative intervention indicated	Death
10038079	Gastrointestinal disorders	Rectal stenosis	Asymptomatic; clinical or diagnostic observations only; intervention not indicated	Symptomatic; altered GI function	Severely altered GI function; tube feeding or hospitalization indicated; elective operative intervention indicated	Life-threatening consequences; urgent operative intervention indicated	Death
10038080	Gastrointestinal disorders	Rectal ulcer	Asymptomatic; clinical or diagnostic observations only; intervention not indicated	Symptomatic; altered GI function (e.g., altered dietary habits, vomiting, diarrhea)	Severely altered GI function; TPN indicated; elective invasive intervention indicated	Life-threatening consequences; urgent operative intervention indicated	Death
10063575	Renal and urinary disorders	Bladder perforation	-	Invasive intervention not indicated	Invasive intervention indicated	Life-threatening consequences; organ failure; urgent operative intervention indicated	Death
10048994	Renal and urinary disorders	Bladder spasm	Intervention not indicated	Antispasmodics indicated	Hospitalization indicated	-	-
10063057	Renal and urinary disorders	Cystitis noninfective	Microscopic hematuria; minimal increase in frequency, urgency, dysuria, or nocturia; new onset of incontinence	Moderate hematuria; moderate increase in frequency, urgency, dysuria, nocturia or incontinence; urinary catheter placement or bladder irrigation indicated; limiting instrumental ADL	Gross hematuria; transfusion, IV medications, or hospitalization indicated; elective invasive intervention indicated	Life-threatening consequences; urgent invasive intervention indicated	Death
10013990	Renal and urinary disorders	Dysuria	Present	-	-	-	-
10068405	Renal and urinary disorders	Glucosuria	Present	-	- Gross hematuria; transfusion, IV medications,	- Life-threatening consequences;	-
10019450	Renal and urinary disorders	Hematuria	Asymptomatic; clinical or diagnostic observations only; intervention not indicated	Symptomatic; urinary catheter or bladder irrigation indicated; limiting instrumental ADL	or hospitalization indicated; lective invasive intervention indicated; limiting self care ADL	urgent invasive intervention indicated Life-threatening consequences;	Death
10065368	Renal and urinary disorders	Urinary fistula	-	Symptomatic, invasive intervention not indicated Limiting instrumental ADL; medical management	Invasive intervention indicated	urgent invasive intervention indicated	Death
10046539	Renal and urinary disorders	Urinary frequency Urinary incontinence	Present Occasional (e.g., with coughing, sneezing,	indicated Spontaneous; pads indicated; limiting	- Intervention indicated (e.g., clamp, collagen injections); operative intervention indicated;	-	-
10040543	nenal and urinary disorders	or intary incontinence	etc.), pads not indicated Urinary, suprapubic or intermittent catheter	instrumental ADL Placement of urinary, suprapubic or intermittent	injections); operative intervention indicated; limiting self care ADL Elective invasive intervention indicated;	- Life-threatening consequences;	-
10046555	Renal and urinary disorders	Urinary retention	placement not indicated; able to void with some residual	catheter placement indicated; medication indicated	substantial loss of affected kidney function or mass	organ failure; urgent operative intervention indicated	Death
10061574	Renal and urinary disorders	Urinary tract obstruction	Asymptomatic; clinical or diagnostic observations only; intervention not indicated	Symptomatic but no hydronephrosis, sepsis, or renal dysfunction; urethral dilation, urinary or suprapubic catheter indicated	Altered organ function (e.g., hydronephrosis or renal dysfunction); invasive intervention indicated	Life-threatening consequences; urgent intervention indicated	Death
	Renal and urinary disorders	Urinary tract pain	Mild pain	Moderate pain; limiting instrumental ADL Limiting instrumental ADL; medical management	Severe pain; limiting self care ADL	-	-
10046593	Renal and urinary disorders	Urinary urgency	Present	Limiting instrumental ADL; medical management indicated	-	•	-
10046628	Renal and urinary disorders	Urine discoloration	Present	-	-	-	-

A.4 Quality of Life according to EPIC-26

The Expanded Prostate Cancer Index Composite (EPIC-26) scoring protocol was designed to measure Quality of Life issues in patients with Prostate cancer.

1. Ove	er the past 4 weeks, how often hav	ve you le	eaked urine?			
	More than once a day		1			
	About once a day		2			
	More than once a week		3 (Circle	e one numbe	er)	
	About once a week		4			
	Rarely or never		5			
2. Which	ch of the following best describes y	our urin	ary control du	ring the las	t 4 weeks?	
	No urinary control whatsoeve	•r		1		
	Frequent dribbling			2	(Circle one nu	umber)
	Occasional dribbling			3		
	Total control			4		
	/ many pads or adult diapers per da ring the last 4 weeks?	ay did y	ou usually use	to control le	eakage	
	None			0		
	1 pad per day			1		
	2 pads per day			2	(Circle one nu	umber)
	3 or more pads per day			3		
4. How	big a problem, if any, has each of	the follo	wing been for	you during	the last 4 wee	ks?
	(Circle one number on each line)					
	Annual and the second sec	No roblem	Very Small Problem	Small Problem	Moderate Problem	Big Problem
a.	11 5 5	0	1	2	3	4
b.	3	0	1	2	3	4
с.	9	0	1	2	3	4
d.	Weak urine stream				-	
	or incomplete emptying		1	2	3	4
e.	Need to urinate frequently during	1				

5. Overall, how big a problem has your urinary function been for you during the last 4 weeks?

1

No problem1
Very small problem2
Small problem3
Moderate problem 4
Big problem5

the day..... 0

(Circle one number)

3

4

2

LCCC 1908 PI: [name]

CONFIDENTIAL UNIVERSITY OF NORTH CAROLINA July 24, 2024

6. How big a problem, if any, has each of the following been for you? (Circle one number on each line)

		No Problem	Very Small Problem	Small Problem	Moderate Problem	Big Problem
a.	Urgency to have					
	a bowel movement	0	1	2	3	4
b.	Increased frequency of					
	bowel movements	0	1	2	3	4
c.	Losing control of your stools	. 0	1	2	3	4
d.	Bloody stools	0	1	2	3	4
e.	Abdominal/ Pelvic/Rectal pain	0	1	2	3	4

7. Overall, how big a problem have your bowel habits been for you during the last 4 weeks?

No problem	1
Very small problem	2
Small problem	3
Moderate problem	4
Big problem	5

(Circle one number)

8. How would you rate each of the following during the last 4 weeks? (Circle one number on each line)

	Very Poor to None	Poor	Fair	Good	Very Good
a. Your ability to have an erection?	1	2	3	4	5
b. Your ability to reach orgasm (climax)?	1	2	3	4	5
9. How would you describe the usual QUALITY of your erections du	uring t	he last	4 wee	ks?	
None at all		. 1			
Not firm enough for any sexual activity		. 2			
Firm enough for masturbation and foreplay only		3	(Circ	le one r	iumber)
Firm enough for intercourse		. 4			
10. How would you describe the FREQUENCY of your erections du	ring th	e last	4 weel	ks?	
I NEVER had an erection when I wanted one		1			
I had an erection LESS THAN HALF the time I wanted one		2			
I had an erection ABOUT HALF the time I wanted one		. 3	(Circ	le one r	number)
I had an erection MORE THAN HALF the time I wanted one.		. 4			
I had an erection WHENEVER I wanted one		. 5			

11. Overall, how would you rate your ability to function sexually during the last 4 weeks?

Very poor	1	
Poor	2	
Fair	3	(Circle one number)
Good	4	
Very good	5	

12. Overall, how big a problem has your sexual function or lack of sexual function been for you during the last 4 weeks?

1	
2	
3	(Circle one number)
4	
5	
	1 2 3 4 5

13. How big a problem **during the last 4 weeks**, if any, has each of the following been for you? (Circle one number on each line)

		No Problem	Very Small Problem	Small Problem	Moderate Problem	Big Problem
a.	Hot flashes	. 0	1	2	3	4
b.	Breast tenderness/enlargement	0	1	2	3	4
C.	Feeling depressed	. 0	1	2	3	4
d.	Lack of energy	. 0	1	2	3	4
e.	Change in body weight	. 0	1	2	3	4

A.5 The local Quality of Life questionnaire

Prostate Cancer Symptom Indices (PCSI): The Quality of Life (QoL) questionnaire that is given to the patients before the beginning of their radiation therapy.

rostate Symptoms She Date:	et				NA	ME:	1	The Man	
Current Dose: (Baselind (Follow up)	e) (In Treatm	ent	cGy)						
Rectal Symptoms: In the	past week have	you			L				
1. Had diarrhea or loose wat stools?	ery Not at all	Occasionally (Once or twice) 2		Frequently eral times) 3		equently t once a day) 4		Very Frequently everal times a day) 5	
2. Had a sense of urgency t you move your bowels?	hat Not at all	Occasionally (Once or twice) 2						Very Frequently everal times a day) 5	
3. Had any tenderness or par when you move your bowel		Occasionally (Once or twice) 2	Fairly Frequently (several times) 3		Frequently (at least once a day) 4		Very Frequently (Several times a day) 5		
4. Had bleeding with your bowel movements?	Not at all	Occasionally (Once or twice) 2		Frequently eral times) 3	Frequently (at least once a day) 4		Very Frequently (Several times a day) 5		
5. Had abdominal cramping pain?	or Not at all	Occasionally (Once or twice) 2	(Once or twice) (seve		Frequently (at least once a day) 4		Very Frequently (Several times a day) 5		
6. Passed mucus from your rectum?	Not at all	Occasionally (Once or twice) 2		Frequently eral times) 3		equently t once a day) (S		Very Frequently Several times a day) 5	
7. Had the urge to move you bowels, but had nothing to	r Not at all 1	Occasionally (Once or twice) 2	Once or twice) (seve		eral times) (at least on		quently Ver once a day) (Seven		
Urinary Symptoms: In the	e past week		S.M.	123.44	to l'anni		1	and the second second	
1. How easy has your urine flow been?	Very Easy 1	Fairly Ea 2	Fairly Easy 2		Slow, but I don't have to strain or bear down 3		d I do or bear	Very slow, and I has to strain or bear dow hard 5	
2. How often did you urinate at night?	Seldom or Neve 1	er Once a Ni 2	Once a Night 2		2 to 3 times a night 3		imes a		
3. How often did you urinate?	4 or fewer times day 1	a 5 to 8 times 2	5 to 8 times a day 2 to 12 tin 2 3		ies a day	day More than 12 times day 4		a	
4. How often have you felt . pain or burning during urination?	Not at all 1		Occasionally (once or twice) 2		Fairly frequently (several times) 3		ly a day)	Very frequently (several times a day 5	
5. How often did you have the feeling that it is urgent that you pass your urine?	Not at all 1		Occasionally (once or twice) 2		Fairly frequently (several times) 3		ontrol	Very frequently 5	
a per ser s de	Had complete control (no leakin 1				Leaked urine most of the time 3		ontrol		
